11.6 Immunogenicity Analyses

All Immunogenicity analysis will be performed using the SS based on all treated subjects.

11.6.1 Primary Endpoint

11.6.1.1 Incidence of Treatment-Induced Anti-Insulin Antibodies

Incidence of treatment-induced AIA is defined as subjects develop newly confirmed positive AIA or have important (4-fold) increase in AIA titer up to visit Week 26. The objective of the primary immunogenicity analysis will be to evaluate equivalence of Gan & Lee Insulin Glargine Injection to Lantus® by comparing the limits of the 90% confidence interval (CI) of difference in proportion of treatment-induced AIA development to the specified margins (-margin, +margin) where the margin is dependent on the unadjusted treatment-induced AIA rate in Lantus® and is defined in Section 5.1, Table 3.

The estimand of interest for the primary immunogenicity analysis is the difference in treatment-induced AIA rates regardless if all subjects tolerate or adhere to study treatment or receive other insulin treatments. Intercurrent events will be handled according to the treatment policy strategy. Treatment Policy strategy is defined as the strategy that considers "The occurrence of the intercurrent event is irrelevant: the value for the variable of interest is used regardless of whether or not the intercurrent event occurs" (See ICH E9 R1 addendum). All AIA data collected, scheduled and unscheduled, will be considered for the analysis, even if collected after the occurrence of intercurrent events of (1) discontinuing study treatment, (2) returning to initial treatment and/or (3) initiating a new treatment.

Any treatment-induced AIA after baseline and up to visit Week 26 will have the subject count as treatment-induced AIA for the primary endpoint. For subjects who have no AIA measurement at scheduled visit Week 12 or 26, AIA measurements from returned visits that fall within the allowed visit window (visit Week 12 ± 1 week or visit Week 26 ± 4 weeks, defined in Section 7.1) will be assigned to the respective time point.

Missing data will be handled as described in Section 11.6.1.2. The SS will be used for the primary analysis.

The number and percentage of subjects in each treatment group who develop treatment-induced AIA as defined in Section 7.2 after baseline and up to visit Week 26 (upper limit of the visit window) will be evaluated using a logistic regression model in proportions along with the corresponding 90% CI.

Equivalence in difference in proportion δ between Gan & Lee Insulin Glargine Injection (π_1) and Lantus® (π_2) will be tested by comparing the limits of the 90% CI for treatment-induced AIA development with the following null hypothesis:

$$H_0: (\pi_1 - \pi_2) \leq -\delta_0 \text{ or } (\pi_1 - \pi_2) \geq \delta_0$$

Against the alternative hypothesis of:

$$H_1: -\delta_0 < (\pi_1 - \pi_2) < \delta_0$$

where δ_0 is the margin dependent on the observed unadjusted treatment-induced AIA rate in Lantus® (π_2) and is defined in Section 5.1, Table 3.

To evaluate equivalence of Gan & Lee Insulin Glargine Injection to Lantus® the calculated 90% CI has to be entirely contained with the interval $(-\delta_0, \delta_0)$.

A sample SAS code fragment is provided below for reference:

```
proc logistic data=<data>;
    class trt / param=ref ref='Lantus';
    model response=trt;
run;
```

The Fisher scoring algorithm will be used for maximum likelihood estimation of the regression parameters. The difference in proportions along with the corresponding 90% CI in the SS using a logistic regression model will be calculated. The delta method will be used to calculate the standard error for the difference and the associated confidence interval (Ge M, Durham LK, Meyer RD 2011 (4)).

Subjects were randomly assigned to treatment using variable block size (See Section 5.2). Blocking should be taken into account when the intra-block correlation is non-zero (Matts and Lachin 1988 (5)). An intra-block correlation of zero can be safely ignored in the analysis (Efird 2011 (6)). Subjects are generally anticipated to remain within sites so the intra-block correlation within investigative site can be assumed to be zero and therefore no adjustment for block is planned.

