### **12.2 Sample Size Estimation**

Enrollment is planned for 550 subjects overall (275 subjects per treatment group). The primary analysis for immunogenicity will be an equivalence test using the 2 one-sided tests (TOST) approach with  $\alpha=0.05$ . This sample size was chosen to achieve over 80% power on the equivalence test of proportion of subjects under the margins dependent on the observed treatment-induced AIA rate. For example, a sample size of 550 will provide approximately 85% power on the equivalence test of proportion of subjects with treatment-induced AIA using an event rate of 30% and a margin of 12% (Table 4). The treatment-induced AIA is defined as newly confirmed positive AIA development or important (at least a 4-fold) increase in AIA titers, after baseline and up to visit Week 26. For this sample size of 550, no dropouts are considered in the calculation. Subjects will be encouraged to come back for assessments even if they have discontinued treatment early.

The similarity margin, based on the actual observed event rate for the intended reference product, will be used for final analysis after database lock as summarized in Table 4. Linear interpolation will be used for values between AIA rates in the table.

**Table 4: Similarity Margins for Actual Observed Event Rate of Proposed Biosimilar to Insulin Glargine for Various Immunogenicity Event Rates**

Treatment-induced AIA Rate for the Reference Product	Margin	Power
10%	7.9%	83%
15%	9.3%	83%
20%	10.5%	84%
25%	11.3%	84%
30%	12.0%	85%
35%	12.5%	85%
40%	12.8%	85%
45%	13.0%	85%
50%	13.1%	85%
55%	13.0%	85%
60%	12.8%	85%
65%	12.5%	85%
70%	12.0%	85%
75%	11.3%	84%
80%	10.5%	84%
85%	9.3%	83%
90%	7.9%	83%

AIA = anti-insulin antibodies.

Sample size calculations were performed using EAST Version 6.4.

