## **12.7 Primary Endpoint**

### **12.7.1 Incidence of Treatment-Induced Anti-Insulin Antibodies**

The primary analysis for immunogenicity will be an equivalence test using the TOST approach with  $\alpha=0.05$ , which is algebraically equivalent to comparing the limits of the 90% confidence interval (CI) for treatment-induced AIA development via a test of difference in proportions based on normal approximation to (-margin, +margin) where the margin is dependent on the observed treatment-induced AIA rate in Lantus® and is defined in [Table 4](#). The estimand of interest for the primary immunogenicity analysis is the difference in treatment-induced AIA rates regardless if all subjects tolerate or adhere to study treatment or receive other insulin treatments. Intercurrent events will be handled according to the treatment policy strategy. Treatment Policy strategy is defined as the strategy that considers “The occurrence of the intercurrent event is irrelevant: the value for the variable of interest is used regardless of whether or not the intercurrent event occurs” (See ICH E9 R1 addendum [16]). Sensitivity analyses including worst-case imputation and using a ‘Composite Strategy’ will be conducted.

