3.1 Changes from Protocol

Per FDA comment, Wald method has been replaced with logistic regression approach to calculate the difference in proportions along with the corresponding 90% CI for the primary endpoint and corresponding sensitivity analyses. The delta method will be used to calculate the standard error for the difference and the associated confidence interval.

Also, per FDA suggestion, separately in each treatment group, the imputation will use outcomes in patients who discontinued treatment but provided a visit Week 26 glycosylated hemoglobin (HbA1c) measurement if sufficient data are available to impute outcomes in patients without actual visit Week 26 recorded results, under the assumption of missing not at random (MNAR). Full details are provided in Section 11.7 below.

4. Study Objectives

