4.3 Exploratory Objective

- To investigate the retrospective hypoglycemic rate and time in hypoglycemia and hyperglycemia using continuous glucose monitoring (CGM) data

5. Study Design

This open-label, randomized, multicenter study is designed to compare the immunogenicity, efficacy, and safety of Gan & Lee Insulin Glargine Injection compared with that of Lantus® in subjects with Type 2 diabetes mellitus to determine equivalence.

Subjects between the ages of 18 and 75 who meet the study inclusion criteria and none of the exclusion criteria as defined in the protocol, will be centrally randomly assigned in a 1:1 allocation ratio to receive either Gan & Lee Insulin Glargine Injection or Lantus®. Randomization and the level of blinding in this study are further described in Section 5.2. Subjects will participate for 2 weeks' screening + 26 week treatment + 4 week following up in total a maximum of 32 weeks in the study. Recruitment will stop when approximately 275 subjects have been randomly assigned to each treatment group. The study will end when the last subject completes the end-of-study visit, or discontinues the study treatment, whichever occurs first.

During the 2 weeks between screening and randomization, once subjects already on basal insulin are determined eligible for the study, they will have their insulin dosing optimized according to Table 1. They will also have any appropriate adjustments in their other antidiabetes medication (OAM) dosing that may

be required because of the optimization of their insulin dosing. Subjects who are insulin-naïve will have their OAM dosing optimized to prepare them for starting basal insulin therapy.

Table 1: Basal Insulin Dose Adjustment Based on Fasting Glucose Result between Screening and Randomization

Lowest Average Fasting Plasma Glucose (Pre-Breakfast) Value for 3 Days	Adjust Basal Insulin Dose (Units per Dose)
> 271 mg/dL (> 15.1 mmol/L)	+ 6 U
181 – 270 mg/dL (> 10.1 – 15.0 mmol/L)	+ 4 U
151 – 180 mg/dL (> 8.4 – 10.0 mmol/L)	+ 2 U
131 – 150 mg/dL (> 7.3 – 8.3 mmol/L)	+ 1 U
71 – 130 mg/dL (> 3.9 – 7.2 mmol/L) (Target Level)	Maintain Current Dose
56 – 70 mg/dL (3.1 – 3.9 mmol/L)	- 2 U
< 56 mg/dL (< 3.1 mmol/L)	- 4 U

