5.1 Sample Size and Power

Enrollment was planned for 550 subjects overall (275 subjects per treatment group). The primary analysis for immunogenicity primary endpoint was to be an equivalence test for the difference in proportion of subjects who develop treatment-induced AIAs between Gan & Lee insulin Glargine Injection and Lantus® using the 2 Wald one-sided tests (TOST) approach with $\alpha=0.05$ (Chow and Shao 2002 (1)). After scientific and regulatory review, the method to evaluate immunogenicity equivalence will be the 90% confidence intervals of risk difference from logistic regression analysis (see Section 3.1). Under this newly adopted approach, no power loss is expected.

This sample size of 275 subjects per treatment group was chosen to achieve over 80% power using the TOST equivalence test for two proportions, a risk difference of zero and equivalence margins dependent on the observed treatment-induced AIA rate per Table 3 below. For example, a sample size of 550 will provide approximately 85% power for the TOST equivalence test using a treatment-induced AIA rate of 30% and a margin of 12% (See Table 3). The treatment-induced AIA is defined as newly confirmed positive AIA development or important (at least a 4-fold) increase in AIA titers, after baseline and up to visit Week 26 (see the definition of Primary Endpoint in Section 6.1 and Section 7.2). No drop outs are considered in the calculation. A larger than expected early discontinuation rate was observed as part of study monitoring activities and therefore protocol amendment 3 approved on 25-Apr-2019 included procedures to encourage subjects to return for assessments even if they have discontinued treatment early.

The appropriate similarity margin, based on the actual observed event rate for the intended reference product, will be used for final analysis after database lock as summarized in the Table 3 below. The power calculation in the table was adapted for a sample size of 550 using the treatment-induced AIA rate for the reference product. Linear interpolation will be used for values between AIA rates in the table.

Sponsor: Gan & Lee Pharmaceuticals, USA Corporation
Protocol no: GL-GLAT2-3002

Statistical Analysis Plan
Version Date: 16-Nov-2020

Table 3: Similarity margins for actual observed event rate of proposed biosimilar to insulin glargine for various immunogenicity event rates

Treatment-induced AIA Rate for the Reference Product	Margin	Power
10%	7.9%	83%
15%	9.3%	83%

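### Reading the equivalence margin from the observed Lantus rate, with a standard error for the difference only, puts the one-sided error for a more immunogenic test product modestly above 0.05 at analysed Lantus rates of about 30% or less

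*SAP*

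**What the plan says.** SAP 11.6.1.1 writes the null as a difference of at least δ0 in either direction. It says that δ0 "is the margin dependent on the observed unadjusted treatment-induced AIA rate in Lantus", written there with the symbol π_2, and declares equivalence when the 90% CI lies wholly inside (−δ0, δ0). On precision it says: "The delta method will be used to calculate the standard error for the difference and the associated confidence interval".

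The margin comes from SAP Table 3 (protocol Table 4), "based on the actual observed event rate for the intended reference product". Between rows, "Linear interpolation will be used for values between AIA rates in the table".

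Protocol 12.2 and 12.7.1 attach alpha = 0.05 to this test without qualification. SAP 5.1 gives alpha = 0.05 only for the Wald TOST that had been planned and states the current method as a 90% CI. SAP 3.1 explains the change: "Per FDA comment, Wald method has been replaced with logistic regression approach to calculate the difference in proportions".

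Neither document gives the type I error of the rule with an observed-rate margin.

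**The concern.** Below 50% the Table 3 margin rises with the Lantus rate. A chance-high Lantus result therefore helps twice: it lowers the observed difference, and it widens the limit that the difference must stay under. The standard error allows for the first effect only, and the interval is compared with the margin as if the margin were a constant. Above 50% the margin falls with the rate, and the same mechanism works on the other side.

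At stake is the error rate of the primary test in the direction that matters most for a biosimilar: declaring equivalence when the test product is more immunogenic by the full margin.

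**Working it through.** **Inputs**
- 275 per arm, 1:1 (SAP 5.1).
- Margins from SAP Table 3, with linear interpolation.
- 90% CI, so z = 1.645.
- The SAP model has treatment as its only term, so its fitted probabilities are the observed proportions and the delta-method SE is the unpooled one: SE = sqrt(p1q1/n1 + p2q2/n2).

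**Assumptions**
- The null boundary is the Table 3 margin m at the true analysed Lantus rate p2.
- The margin is flat outside 10–90%, where the table is silent. No result is claimed below 15%.

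**1. The plan's own figure.** At 30% in both arms with margin 12%, SE = sqrt(2 × 0.3 × 0.7 / 275) = 0.0391. Power = 2Φ(0.12/0.0391 − 1.645) − 1 = 84.6%, against about 85% stated. Exact binomial power with a fixed margin is 84.9%. The set-up matches the sponsor's.

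**2. Slope s of Table 3.** 15–20%: (10.5 − 9.3)/5 = 0.24. 20–25%: 0.16. 25–30%: 0.14. 30–35%: 0.10. 35–40%: 0.06. 40–45%: 0.04.

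**3. Large-sample check.** The upper test rests on p1 − p2 − m(p2), whose variance is p1q1/n + (1+s)²p2q2/n. The plan uses p1q1/n + p2q2/n. At the boundary:

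upper error ≈ Φ(−1.645 × sqrt[(p1q1 + p2q2) / (p1q1 + (1+s)²p2q2)])

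Upper errors arise mainly when the Lantus rate is observed high, so s is taken from the segment to the right.
- 30%: p1 = 0.42, s = 0.10. sqrt(0.4536/0.4977) = 0.955, and Φ(−1.570) = 5.8%.
- 20%: p1 = 0.305, s = 0.16. sqrt(0.3720/0.4273) = 0.933, and Φ(−1.535) = 6.2%.

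The sample size cancels, so a larger trial would not remove the excess.

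**4. Exact enumeration of both binomials, 275 per arm.** Error is evaluated at p1 = p2 ± m, and both one-sided conditions are required.

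| Analysed Lantus rate | Upper, SAP rule | Upper, fixed margin | Lower, SAP rule |
|---|---|---|---|
| 15% | 6.9% | 5.1% | 2.4% |
| 20% | 6.3% | 5.1% | 2.8% |
| 25% | 6.1% | 5.0% | 3.5% |
| 30% | 5.8% | 4.9% | 3.8% |
| 35% | 5.4% | 5.0% | 4.0% |
| 40% | 5.4% | 4.9% | 4.4% |
| 45% | 4.9% | 4.9% | 4.5% |
| 50% | 4.5% | 4.9% | 4.5% |

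From about 40.5% to 47% the two upper columns agree. The pattern mirrors above 50%: lower error is 5.8% at 70% and 6.3% at 80%.

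**5. Is it discreteness?** The SAP says: "Recruitment will stop when approximately 275 subjects have been randomly assigned to each treatment group". Arm sizes will therefore vary, so 64 pairs were run, with each arm from 268 to 282 in steps of 2.

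| Rate | SAP rule, mean (range) | Fixed margin, mean (range) |
|---|---|---|
| 20% | 6.22% (5.94–6.46) | 5.02% (4.81–5.15) |
| 25% | 6.08% (5.85–6.37) | 4.98% (4.80–5.28) |
| 30% | 5.74% (5.46–6.08) | 4.95% (4.59–5.29) |
| 35% | 5.42% (5.01–5.75) | 4.94% (4.61–5.31) |

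At 40% the means are 5.22% and 4.93%. The ranges are separate at 20 to 30% and overlap at 35% and 40%.

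**6. Missing samples counted as positive (SAP 11.6.1.2, Table 4).** The analysed rate is r + f(1 − r) for true rate r and missing fraction f. The documents give neither, so both are assumed, with f equal in the two arms.
- r = 30%, f = 0, 5, 10, 15, 20%: analysed 30.0, 33.5, 37.0, 40.5, 44.0%. Upper error 5.8, 5.4, 5.5, 5.3, 5.0%, against 4.9, 5.1, 4.8, 5.3, 5.0% with a fixed margin.
- r = 15%, f = 0, 10, 20%: analysed 15.0, 23.5, 32.0%. Upper error 6.9, 6.2, 5.6%, against 5.1, 5.0, 4.9%.

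**7. Slope-corrected tests.** Multiplying the Lantus variance term by (1+s)² for the upper test and (1−s)² for the lower gives upper error 4.9%, 5.0% and 4.9% at 20%, 30% and 40%, with power 82.4%, 83.8% and 84.3%. Over 12–85%, upper error is 4.7–5.4%, lower error 4.0–5.4% and power 81.9–84.7%.

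**The case against.** **The null is the reviewer's.** The documents define the margin only through the observed rate, so they omit an operating characteristic rather than contradict themselves. That is fair, and the result is conditional on the reading. But a null that depends on the data has no type I error until a boundary is fixed, and SAP 11.6.1.1 ties the margin to π_2. The true-rate reading is the natural one.

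**The practical size is small.** The true difference at which the SAP rule's upper error is exactly 5% is 12.3 points against a margin of 12.0 at 30%, and 10.9 against 10.5 at 20%. A fixed-margin Wald test is not exact either: its lower error is 5.4% at 15%. Both points stand, and they limit the weight of the finding.

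**The trial may not sit in the affected range.** The 30% rate is only an example. SAP 5.1 also reports: "A larger than expected early discontinuation rate was observed as part of study monitoring activities". With missing samples counted as positive, that pushes the analysed rate up. This stands too, although a low true rate would remain affected.

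**The agency has reviewed the method.** The change recorded in SAP 3.1 is from Wald to logistic regression. With treatment as the only term, the SE is the same. The documents record no discussion of sampling error in the margin. Even so, replacing an interval adopted on agency comment is a trade-off and not a plain correction.

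**Stronger readings a reader might infer.** One is that the error is inflated at every rate below about 40%; the overlapping ranges at 35% and 40% do not support that. Another is that protocol 12.7.1 is wrong to call TOST and the CI comparison algebraically equivalent. That duality holds for any margin, observed or fixed, and the wording is correct. A third is that the sensitivity analyses that reuse the primary margin need relabelling. That is a separate matter, and SAP 11.6.1.3 already presents them as sensitivity analyses.

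**Conclusion.** The point holds for analysed Lantus rates of about 30% or less. There the rule exceeds the protocol's 0.05 on the higher-immunogenicity side by 0.9 point at 30% (5.8 against 4.9) and 1.8 points at 15% (6.9 against 5.1), while the opposite side is conservative. At 70% and above the excess is on the lower side.

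This rests on the true-rate null boundary, about 275 per arm and the unpooled SE. It does not show that a conclusion of equivalence would be wrong, or that this trial's analysed rate lies in the affected range. It shows that an unqualified alpha = 0.05 is not a property of the planned test at the documents' own 30% example rate.

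**What to change.** **Text.** In SAP 11.6.1.1, state that the null boundary is the Table 3 margin at the true analysed Lantus rate. In protocol 12.2 and 12.7.1, replace the unqualified alpha = 0.05 for the primary test with the attained upper and lower errors by Lantus rate (the SAP-rule columns in step 4, mirrored above 50%). Put a matching note in the SAP. This costs one table and a few sentences, and the decision rule is unchanged.

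**Supplementary analysis.** Prespecify the two one-sided 0.05 tests with slope-corrected SEs:
- upper: p1 − p2 − m(p2), with SE sqrt(p1q1/n1 + (1+s)²p2q2/n2)
- lower: p1 − p2 + m(p2), with SE sqrt(p1q1/n1 + (1−s)²p2q2/n2)

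Here s is the Table 3 slope at the observed Lantus rate. State which slope applies at a table row (for example, the right-hand segment) and what applies outside 10–90% (for example, a flat margin with s = 0).

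**Decision rule.** Make these tests decisive only if the agency agrees. The price is up to about 2.2 points of power (at 17%), and error of up to about 5.4% near 43% (lower side) and 57% (upper side), where the present rule gives 4.5%.

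Leave the algebraic-equivalence statement in protocol 12.7.1 and the labelling of the sensitivity analyses as they are.

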11.6.1.2 Methods for Handling Dropouts and Missing Data

Utilizing a "Treatment Policy" strategy, missing data (after using data collected during or after treatment, and assigning data to the appropriate scheduled visit as described above) for the primary endpoint will be imputed as per Table 4. Sites have been trained in the importance of collecting baseline AIA samples. In the rare and unlikely event a site does not collect a baseline AIA sample, imputation rule for missing baseline assessment is included in the table. Unscheduled assessments (e.g. EOT documented at visit Week 26 outside the visit windows for discontinued subjects) up to visit Week 26 will be considered in the overall result but will not be imputed.

Table 4: Imputation Rules for Missing Data in Primary Immunogenicity Analysis

Category	Sample Availability	Imputation	Likely Scenarios
1	All three AIA samples collected and analyzed	
 No imputation 	
 Subjects complete the study. Dropout subjects provide the required AIA samples within the defined visit window.
2	At least one AIA sample missing at Week 12 or Week 26 regardless of baseline sample availability	
 Subject will be counted as 'developing a treatment-induced AIA'. 	
 Dropout subjects who are unable to provide AIA samples in respective visit window. AIA sample missing due to protocol deviations.

Category	Sample Availability	Imputation	Likely Scenarios
3	Baseline sample missing, but both Week 12 and Week 26 samples are collected and analyzed	
 Subject will be counted as 'developing a treatment-induced AIA' if any of Week 12 or Week 26 results are positive. Subject will be counted as 'NOT developing a treatment-induced AIA' if both Week 12 and Week 26 results are negative. 	
 Baseline AIA sample missing due to protocol deviations.
4	Any positive results from unscheduled (or out of window) AIA sample(s) during the Treatment Period	
 Positive result from unscheduled AIA sample will be treated the same way as the Week 12/26 samples when baseline result is present. Positive result from unscheduled AIA sample will render the subject as 'developing a treatment-induced AIA' if baseline sample is missing. 	
 Sample collection out of the allowable sample collection window. Sample collection due to other protocol deviations.

